4.2 Scientific Rationale for Study Design

This study will assess the performance of and user experience with PureWick[™] System in a home setting. The endpoints chosen for the study were selected based on peer-reviewed research and feedback from expert consultants, Centers for Medicare & Medicaid Services, applicable health authorities and urology key opinion leaders.

To best mimic potential users of the PureWickTM System, participants \geq 18 years of age will be enrolled with a target of at approximately 90% of participants \geq 65 years of age. The treatment duration of 4 weeks for each investigational device was selected to allow sufficient time for a potential impact to quality of life. For this study, the baseline quality of life scores will be compared to mid-treatment scores and to post-treatment scores.

The PureWickTM System may provide improvements to urine output management, specifically in the home-setting. Additionally, the PureWickTM At-Home study is required to provide the needed information to properly execute a future global randomized control trial (RCT) with confidence of success.

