7.2.7 Days 2-7

- 1. Prior to nurse visit, participants are expected to have placed the used night pads and mesh underwear (if applicable) in their respective labeled, pre-weighed sealed bag upon completion of sleep.
- 2. Nurse will weigh and document weight of night pads and mesh underwear (if applicable).
- 3. The nurse will weigh and document the captured urine.
 - For PureWickTM Treatment Phase the captured urine volume in the PW urine collection canister will be weighed and documented.
 - For Hollister_® FUP Treatment Phase the captured urine volume in the bedside urine bag will be emptied into a graduated cylinder, then weighed and documented.
- 4. The nurse will note any signs of skin irritation or injury and document the Draize Scale score*
- 5. If during the skin assessment a Draize score of 4 is documented on the skin irritation scale in any category, this must be recorded as an AE and will require participants to discontinue from the treatment phase; participant will immediately begin wash out period and complete N-QoL.
- 6. Nurse will pre-weigh and document weight of study supplies for next night use.
- 7. The nurse will confirm the next day visit.

* For safety assessment, see section 7.3

7.2.8 Day 8

- 1. Same procedures as days 2-7.
- 2. Participant to complete Day 8 PROMIS Sleep Disturbance assessment.

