Study ID: UCC-8007	Version No: 01

*To be completed per treatment schedule or upon treatment discontinuation, whichever comes first.

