The questionnaire will be completed on Day 1, Day 15 and Day 29 of both study phases. We will categorize the questionnaire timepoint as baseline, week 1-2 (day 2-17) and week 3-4 (> day 17), respectively. If day 15 is missing, the latest record between day 2 and 17 will be used for week 1-2; if day 29 is missing, the latest record after day 17 will be used for week 3-4. Descriptive statistics will be provided by each questionnaire timepoint, treatment, and phase. A scatter plot for N-QoL (y axis) vs. Day # (x axis), with different colors representing PureWick and Hollister and different panels representing study subject will also be provided. Linear mixed model may be used, with treatment, phase, and day number as the fixed effect, and participant as the random effect.

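### SAP 5.2.3.1 keeps the N-QoL scores of women who stop a device by Day 17 out of week 3-4, the only summary that can serve as the post-treatment comparison

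*SAP*

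**What the plan says.** Protocol 4.2 sets the quality-of-life aim: "the baseline quality of life scores will be compared to mid-treatment scores and to post-treatment scores". The N-QoL is scheduled on Days 1, 15 and 29 of each phase. The footnote to the schedule of activities (protocol 1.3, repeated in SAP 2.6) adds: "To be completed per treatment schedule or upon treatment discontinuation, whichever comes first". For a stop caused by a Draize score of 4, protocol 7.2.7 says the "participant will immediately begin wash out period and complete N-QoL".

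SAP 5.2.3.1 then assigns the post-baseline scores to "week 1-2 (day 2-17) and week 3-4 (> day 17), respectively". Two rules fill gaps. For the first timepoint: "If day 15 is missing, the latest record between day 2 and 17 will be used for week 1-2". For the second: "if day 29 is missing, the latest record after day 17 will be used for week 3-4". The reporting commitment is: "Descriptive statistics will be provided by each questionnaire timepoint, treatment, and phase". A per-subject plot of N-QoL against day is also promised. The model is optional: "Linear mixed model may be used, with treatment, phase, and day number as the fixed effect, and participant as the random effect".

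SAP 4.1 assigns the ITT population to the endpoint analyses. SAP 5.2.1.1 gives missing-data methods for the two primary endpoints only.

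**The concern.** Week 3-4 can be filled only by a form dated after Day 17. A woman who gives up a device before then has normally completed her last N-QoL for that phase, so she cannot appear in week 3-4. Membership of that summary therefore depends on how long she wore the device, which is an event after randomization.

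The missing scores are unlikely to be a random subset. Stopping for discomfort or inconvenience is itself a secondary tolerability endpoint, and a Draize score of 4 ends the phase. If one device has more early stops, and those women rate their quality of life lower, its week 3-4 mean rests on its more satisfied users. The same selection carries into SAP 5.2.4.2, where the week 3-4 plot of N-QoL against maximum Draize score would lack women stopped by a Draize 4 by Day 17. The sponsor intends the data to support reimbursement and to inform the later randomized trial, so a flattering later-period mean could be carried forward.

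**Working it through.** The plan gives no effect size, power or early-stop rate for N-QoL, so there is no figure of its own to reproduce. The check has two parts.

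**Where each stop score goes.** Inputs are the windows and gap rules in SAP 5.2.3.1 and the collection rule in the schedule footnote. Assume each woman completes the scheduled forms she reaches, plus one on the day she stops.

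| Stop day | Week 1-2 filled by | Week 3-4 filled by | Stop score reported in |
|---|---|---|---|
| 2-14 | stop score | nothing | week 1-2 only |
| 15 | Day 15 form, which is the stop score | nothing | week 1-2 only |
| 16-17 | Day 15 form | nothing | neither timepoint |
| 18-28 | Day 15 form | stop score | week 3-4 |

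Of the 16 possible stop days from 2 to 17, 14 send the stop score to week 1-2, 2 send it to no timepoint, and 0 send it to week 3-4. All 11 stop days from 18 to 28 reach week 3-4. If a woman stopping on Day 16 or 17 had missed her Day 15 form, her stop score would fill week 1-2.

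**What this could do to a mean.** Let d be the share of women who stop a device by Day 17, and g the gap (mean of the others minus mean of the stoppers) on the 0-100 scale. Neither is in the documents; both are assumed.

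- Week 3-4 mean = mean of the others.
- Mean of everyone's last on-device score = (1 − d) × mean of the others + d × mean of the stoppers.
- Difference = d × g.
- Women left in week 3-4 = 30 × (1 − d), taking about 30 women per device.

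| Assumed d | n in week 3-4 | g = 10 | g = 20 | g = 30 |
|---|---|---|---|---|
| 10% | 27 | 1 | 2 | 3 |
| 20% | 24 | 2 | 4 | 6 |
| 40% | 18 | 4 | 8 | 12 |

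A worked case: 26 women average 65 and 4 early stoppers average 35. The week 3-4 mean is 65.0, and the mean of last scores is (26 × 65 + 4 × 35) / 30 = 61.0. The difference of 4.0 equals (4/30) × 30.

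Between devices with the same g, the shift is the difference in d times g. With 10% stopping one device early and 30% the other, it is 0.20 × 10 to 0.20 × 30, or 2 to 6 points. With equal rates and equal gaps it is 0.

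**The case against.** The SAP calls the timepoint week 3-4, not end of treatment, and an on-device week 3-4 summary properly describes women observed then. Stop scores from Days 2-15 are not lost: they count in week 1-2, under the right device and phase. Even a Day 16-17 stop score can appear in the per-subject plot, which is mandatory, and in the mixed model, which works on day number. Days of use, discontinuation rate and disposition by reason are all reported, so a reader could see that week 3-4 is a selected group. N-QoL is secondary, in a pilot of about 30 with no formal test, and protocol 8.1 expects withdrawal to be uncommon.

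Most of this stands, and it rules out several stronger readings that a reader might infer:

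- **That stop scores are discarded.** Only those from Day 16 or 17 after a completed Day 15 form miss both timepoints.
- **That week 3-4 is a completers' summary.** Women stopping on Days 18-28 are in it.
- **That a planned device difference is biased by a known amount.** No paired N-QoL difference is planned, unlike for capture rate, Draize score and days of use, and neither the early-stop rate nor the score gap is documented.
- **That every stop score is available.** Protocol 8.1 ends assessments when a woman leaves the study, so some may have none.
- **That washout forms will routinely count as on-device scores.** The week 3-4 window has no upper limit, but no N-QoL is scheduled in washout; this is an edge case.

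The objection does not supply a post-treatment summary that includes early stoppers. Protocol 4.2 promises that comparison, week 3-4 is the only timepoint that can provide it, and the model that could use every record is optional.

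**Conclusion.** The point holds as a limited selection problem in a secondary endpoint. The day windows leave women who stop a device by Day 17 out of week 3-4, although their stop score is normally collected. This rests on stop forms being dated when the woman stops; a form completed late, on Day 18 or after, would enter week 3-4.

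The direction is conditional. Week 3-4 means flatter a device only if more women stop it early and those women score lower. The size is unknown. Under an assumed gap of 10-30 points, each 10% stopping early raises that device's week 3-4 mean by 1-3 points above the mean of all last scores. The documents do not support saying that either device will benefit, or by how much. The change is worth making because it uses data already collected.

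**What to change.** In SAP 5.2.3.1:

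1. Keep week 1-2 and week 3-4 as on-device timepoints.
2. Add a supplementary last on-device N-QoL summary by treatment and phase: the Day 29 score or, if the phase ended early, the form completed at discontinuation whatever its day. Show n and days of wear beside it. Where a stop form exists, this brings in all 16 early-stop days; with complete forms, n per device returns from 30 × (1 − d) to 30.
3. Make the mixed model on all N-QoL records definite.
4. Limit week 3-4 to forms completed by the end-of-phase visit. State that the form completed at discontinuation counts as on-device although washout starts then; otherwise the limit could remove the Draize 4 stop form.

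The cost is SAP wording, one table and a model already described. No visit, form or clinical rule changes. The downside is that last on-device scores follow different lengths of wear, so a Day 3 score would sit beside a Day 29 score. The summary should therefore stay supplementary. Women who leave without a form will still be missing from it, and n will show how many.

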5.2.3.2 Questionnaire PROMIS Sleep Disturbance

The questionnaire consists of 4 items with a total raw score ranging from 4 to 20 (sum of the 4 questions). The total raw score will be translated into a T-score for each participant using the score conversion table from the PROMIS sleep scoring manual (Table 3). All questions must be answered in order to produce a valid score using the scoring tables. The T-score rescales the raw score into a standardized score with a mean of 50 and a standard deviation (SD) of 10. Items in the questionnaire will be summarized both as categorical variable (using frequency count and percentage) and as continuous variables (using mean, standard deviation, median, and range) by treatment.

Raw Score	T-score
4	32.0
5	37.5
6	41.1
7	43.8
8	46.2
9	
10	50.5
11	52.4
12	54.3

Table 3. PROMIS Sleep Disturbance 4a - Short Form Conversion Table

	Statistical Ana	alysis Plan	Page No. 15 of 20
BD	Study ID: UCC-8007		Version No: 01
GFM-10082C			
	13	56.1	
	14	57.9	
	15	59.8	
	16	61.7	
	17	63.8	
	18	66.0	
	19	68.8	
	20	73.3	

5.2.3.3 Tolerability - Number of days of actual use

The calculation for the number of days of actual use will involve counting the non-missing records for each device, determined by the number of non-missing Day # entries. Subsequently, the number of days of actual use will be summarized using descriptive statistics by treatment. Paired differences between treatments will also be provided.

5.2.3.4 Tolerability - Discontinuation rate due to device discomfort or inconvenience

Rate of not completing a treatment phase due to device discomfort or inconvenience will be summarized using descriptive statistics.

5.2.3.5 Comfort, Ease of Use and Confidence

Items in the questionnaire will be summarized both as categorical variable (using frequency count and percentage) and as continuous variables (using mean, standard deviation, median, and range) by treatment.

5.2.4 Exploratory Analysis

5.2.4.1 Correlation between capture rate and N-QoL

- Scatter plot:
 - N-QoL (y axis) vs. Capture rate (x axis) for week 1-2, with different colors representing PureWick and Hollister
 - The average nightly capture rate for each subject will be computed and used as x axis
 - N-QoL (y axis) vs. Capture rate (x axis) for week 3-4, with different colors representing PureWick and Hollister
 - The average nightly capture rate for each subject will be computed and used as x axis
- Table: Summary statistics (n, mean, SD, median, min, max) for N-QoL (week 1-2 and week 3-4) by two capture rate groups (<= median vs. > median), the data will be presented separately for PureWick and for Hollister. The calculation for the median capture rate will be as follows: compute the average of nightly capture rate for each subject , then determine the median for week 1-2 (day 1-14) or week 3-4 (day 15-28) for each device.

- 5.2.4.2 Correlation between Draize scale and N-QoL
- Boxplot
 - N-QoL week 1-2 (y axis) vs. Draize scale maximum per subject per device (x axis), with different colors representing PureWick and Hollister
 - N-QoL week 3-4 (y axis) vs. Draize scale maximum per subject per device (x axis), with different colors representing PureWick and Hollister
- Scatter plot
 - N-QoL week 1-2 vs. Draize scale average per subject per device (x axis), with different colors representing PureWick and Hollister
 - N-QoL week 3-4 vs. Draize scale average per subject per device (x axis), with different colors representing PureWick and Hollister
- 5.2.4.3 Correlation between Draize scale and capture rate
- Scatter plot: Capture rate (y axis) vs. Draize scale average per subject per device (x axis), with different colors representing PureWick and Hollister
- Scatter plot: Capture rate (y axis) vs. Draize scale (x axis), with different colors representing PureWick and Hollister and different panels representing study day
- Scatter plot: Capture rate/ Draize scale (y axis) vs. study day (x axis)

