2.4 Sample Size

Approximately 30 participants will be enrolled. The sample size is planned based on operational and practical considerations and is adequate for the purpose of this pilot study.

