5.2.1.3 Multiplicity Control

No formal hypothesis test is planned for this pilot study. P values and confidence intervals may be provided for exploratory purposes and are unadjusted for multiplicity.

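### SAP 5.2.4.1 is headed as a correlation but specifies no estimate: its only numbers come from a device- and window-specific median split, an inefficient summary that should not be read across devices or windows

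*SAP*

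**What the plan says.** SAP 5.2.4.1 carries the title "5.2.4.1 Correlation between capture rate and N-QoL". It lists two kinds of output.

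- **Scatter plots** of N-QoL against capture rate, one for weeks 1-2 and one for weeks 3-4, coloured by device. Capture rate stays continuous: "The average nightly capture rate for each subject will be computed and used as x axis". No coefficient, fitted line or interval is named.
- **One table** of N-QoL summary statistics (count, mean, SD, median and range) for each window, "by two capture rate groups (<= median vs. > median), the data will be presented separately for PureWick and for Hollister". The rule for the cut is to average each woman's nightly rates and "then determine the median for week 1-2 (day 1-14) or week 3-4 (day 15-28) for each device". That allows up to four different cut-points.

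Nothing else in the text supplies an estimate of this association. The optional N-QoL model in SAP 5.2.3.1 reads "Linear mixed model may be used, with treatment, phase, and day number as the fixed effect, and participant as the random effect", so capture rate is not in it. SAP 5.2.1.3 says "P values and confidence intervals may be provided for exploratory purposes and are unadjusted for multiplicity", but ties none to this analysis. On sample size, SAP 2.4 says "Approximately 30 participants will be enrolled".

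**The concern.** Capture rate is a percentage averaged over up to 14 nights per window, so each woman has a near-continuous value. Reducing it to low or high discards the distance from the cut, and the SAP gives no clinical or regulatory reason for doing so. With about 30 women, each group holds about 15.

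Two things follow for someone reading the table. First, a real association can look weak or absent because the summary is imprecise. Second, low and high are relative to each device's own median in that window. A woman with the same capture rate on both devices may be low on one and high on the other, and the low/high N-QoL gap reflects how widely capture varies as well as how strongly it relates to quality of life.

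The table also gives no change in N-QoL per unit of capture, although that is the natural way to express a link between the primary efficacy measure and a secondary quality-of-life score.

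**Working it through.** The documents give no expected correlation, capture distribution or precision figure for this analysis, so there is no planned figure to reproduce. The effect sizes and distributions below are assumptions, shown as ranges.

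**1. Inputs from the SAP.** About 30 women (2.4); a split at or below versus above the median for each device and window (5.2.4.1); capture rate on a 0-100% scale (5.2.2.1). Group size if all are evaluable: 30 / 2 = 15.

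**2. Information kept by a median split.** For a linear association this is the squared correlation between capture rate X and the indicator that X exceeds its median. For normal X, the covariance is SD × 0.399 and the indicator's SD is 0.5. The correlation is therefore 0.399 / 0.5 = 0.798, and 0.798² = 2/π = 0.637. The loss is 36.3%, and 30 × 0.637 = 19.1 women.

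The loss under other assumed shapes, by simulation:

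| Assumed capture distribution | Mean | Loss |
|---|---|---|
| Beta(2,2), symmetric | 50% | 29.7% |
| Beta(8,2) | 80% | 37.6% |
| Beta(9,1) | 90% | 45.6% |
| Beta(2,0.3), strong ceiling | 87% | 57.5% |

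So the loss is about a third under normality and ranges from about 30% to 58% across the shapes tried. It is larger when rates pile up near 100%.

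**3. What that means at n = 30.** Two-sided 5% detection rates, normal data, 8,000 replicates. The split is represented by a two-sample t-test, which the SAP does not plan; it is used only to show the lost precision.

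| True r (assumed) | Pearson | Spearman | Median split |
|---|---|---|---|
| 0.3 | 37% | 33% | 23% |
| 0.4 | 62% | 56% | 42% |
| 0.5 | 83% | 77% | 60% |
| 0.6 | 96% | 92% | 81% |

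A separate run of 20,000 replicates gave Pearson and split rates within about 2 points of these (at r = 0.5, 83% and 61%). In the table, the rank correlation exceeds the split by 33 − 23 = 10 points at r = 0.3 and by 77 − 60 = 17 at r = 0.5. With capture skewed towards its ceiling (Beta(4,1)) and r = 0.5, the three rates are 79%, 76% and 61%.

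**4. The gap depends on spread.** For normal capture, the mean difference in capture between the two halves is 2 × 0.798 × SD. With slope b, the N-QoL gap is 2 × b × SD × 0.798. Take the same assumed slope on both devices, b = 0.5 N-QoL points per capture point:

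- SD 5: 2 × 0.5 × 5 × 0.798 = 4.0 points
- SD 15: 2 × 0.5 × 15 × 0.798 = 12.0 points

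The gaps differ threefold although the relationship is identical.

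**5. The meaning of low depends on the device.** With assumed mean capture of 90% and 80% (beta, concentration 12), the medians are 92% and 82%. About 70% of the low group on the better device lies above the other device's median. With assumed means of 95% and 75% this is about 96%. If the two medians are equal, the cut-points coincide and this part of the problem disappears.

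**6. What a full-scale estimate would deliver.** The Fisher interval at n = 30 is tanh(arctanh(r) ± 1.96/√27). This gives 0.17 to 0.73 at an observed r of 0.5, and −0.07 to 0.60 at 0.3. A rank correlation is slightly less precise: at an observed 0.4 the approximate interval is 0.04 to 0.67.

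**The case against.** The strongest reply is that the table is purely descriptive and supplements scatter plots that discard nothing. Both devices share the same axes there, so a reader can see that 80% capture is 80% on either device. This stands: the loss belongs to the table and not to the section as a whole.

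A reader might infer that a planned test loses power. The documents do not support that: SAP 5.2.1.3 plans no formal test, and the table asks only for summary statistics. A reader might also infer that the SAP intends to compare devices by their low/high gaps. It does not: the results are presented separately by device, and within one device a median gives balanced groups, which is a reasonable display at this size. What remains is a caution about reading the table, because adjacent device tables invite a comparison they cannot support.

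It can also be said that the pilot's stated planning uses are sample size and nursing-visit frequency, and that neither document says an N-QoL slope is needed for either. That stands too. The case for an estimate rests on the section's own title and on its low cost.

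Finally, the table shells in SAP Appendix 1 are not reproduced, so a coefficient there cannot be ruled out. The SAP text specifies none.

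**Conclusion.** The point holds as a minor improvement to an exploratory analysis. SAP 5.2.4.1 promises a correlation and specifies no measure of one. Its only numerical result keeps about 64% of the information if capture rate is roughly normal, and about 42% to 70% across the assumed shapes. Its gaps vary with each device's capture spread and cut-point, so they should not be read across devices or windows. How much the cut-points differ depends on device medians that the documents do not predict.

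It would be too strong to say that the study discards a third of its information on this question, or that its conclusions are underpowered because of the split. The plots keep the full scale, no test is planned and the primary endpoints are unaffected. The detection rates only illustrate lost precision.

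**What to change.** In SAP 5.2.4.1 add, for each device and each window:

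- the Spearman correlation between each woman's mean capture rate and her N-QoL total score, with a 95% CI;
- the linear slope, in N-QoL points per 10 percentage points of capture, with a 95% CI, and a note that it may be sensitive to a few low-capture women if most rates are near the ceiling.

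Name these as the numerical result. The median-split table may stay as a descriptive display if each cut-point value is printed and the table is labelled as not for comparison between devices or windows.

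A single common cut-point may look like the natural remedy, but it can leave sparse cells. Under the assumed means of 95% and 75%, a pooled median near 88% puts only about 4 of 30 women in the low group on one device and about 4 of 30 in the high group on the other. It is not recommended here.

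The cost is a few lines of SAP wording and one procedure call per device and window, with no new data. The downside is one more small exploratory table with wide intervals. SAP 5.2.1.3 already covers these as exploratory and unadjusted.
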